Comparative effectiveness of energy doses in critical illness

Short title: The Energy Dose Study

Principal Investigator: [name].

Protocol Version Date: 6/2/2014

NCT Number: NCT01369147

Abstract:

Protein and/or energy deficits are associated with increased rates of hospital infection, skeletal muscle weakness, impaired wound healing, and prolonged convalescence in ICU patients. To prevent or treat malnutrition, enteral nutrition (EN) and/or parenteral nutrition (PN) are routinely given worldwide to a significant proportion of ICU patients. Optimal caloric requirements in critically ill patients are unknown due to a lack of rigorous randomized clinical trials. The comparative efficacy of energy doses in critically ill patients is unknown and clinical recommendations are conflicting and controversial; this issue is the focus of our study.

We have designed this pilot, single-center Randomized Clinical Trial (RCT) to prospectively compare, for the first time, the clinical efficacy of different energy doses in ICU patients requiring PN due to intestinal failure/dysfunction. A total of 60 patients will be studied (20 per energy dose group) to generate critical preliminary data needed to inform subsequent appropriately powered Phase III multicenter trials.

The primary aim of this study is to perform a controlled, double-blind, prospective, randomized, intent-to-treat Phase II clinical trial to test the efficacy of three specific energy doses [0.6, 1.0 and 1.3 x measured REE (resting energy expenditure), respectively], given for 28 consecutive days during the ICU course, on 28-day total hospital-acquired infections (primary endpoint), Blood Stream Infections (BSI), and other important clinical outcomes in medical/surgical ICU patients requiring specialized parenteral \pm enteral feeding. We would also determine, in these subjects A) the impact of cumulative and mean daily 28-day energy deficits [energy intake-measured REE] on clinical outcome endpoints; and B) the practical utility of estimated REE determined by Harris-Benedict equation versus measured REE across different energy doses. We would also like to determine the impact of administered energy dose and energy deficits on global metabolomic patterns over time and their association with key clinical outcomes.

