Twenty-eight day mortality will be summarized as a proportion plus the 95% confidence interval (overall and for each treatment group). The 28-day mortality will be compared between treatment groups using a chi-square or Fisher's exact test. The potential association of each of the categorical prognostic factors (gender, race, high or low Apache score, clinical center) with mortality will also be evaluated using a Chi-square test or Fisher's exact test. Baseline continuous prognostic factors (age, SOFA score, blood glucose) will be compared by treatment group using the Wilcoxon rank-sum test. Odds ratios will be calculated to measure the degree of association. All statistical tests will be 2-sided. Factors significant to at least a value of $P \leq 0.20$ in the univariable analyses will be used in multivariable logistic regression analyses. Forward and backward stepwise selection will be used if necessary to choose prognostic variables for a multivariable logistic regression model. The odds ratio and its 95% confidence interval will be calculated for each factor in the presence of others in the final model.

Days on mechanical ventilation, length of ICU stay and hospital length of stay will be summarized with percentiles (25th, 50th and 75th) and the median absolute deviation. These secondary outcomes will be compared between the 3 treatment groups using the Kruskal-Wallis test. Repeated-measures analyses of daily SOFA scores and laboratory measures such as blood glucose will be analyzed with a means model with SAS Proc Mixed (version 9, mixed linear models) providing separate estimates of the means by time on study (days 0, 3, 7, 14, 21, and 28) and treatment group (energy dose: 0.6, 1.0 and 1.3 x REE). An unstructured variance-covariance form among the repeated measurements will be assumed for each outcome and estimates of the standard errors of parameters will be used to perform statistical tests and construct 95% confidence intervals. T-tests will be used to compare the pairwise differences between the model-based treatment means (least-squares means) at each time point. Statistical tests will be 2-sided. The model-based means are unbiased with unbalanced and missing data, so long as the missing data are non-informative (missing at random). A dropout process is assumed to be missing at random if; conditional on the observed data, the dropout is independent of the unobserved measurements.

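### SOFA and glucose get 18 unadjusted pairwise t-tests per outcome, and model-based standard errors make the late-visit intervals too narrow if many patients have dropped out

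*Combined protocol and SAP*

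**What the plan says.** Statistical Analysis, For Aim 1, sets out the method: "Repeated-measures analyses of daily SOFA scores and laboratory measures such as blood glucose will be analyzed with a means model". The model gives "separate estimates of the means by time on study (days 0, 3, 7, 14, 21, and 28") and by "treatment group (energy dose: 0.6, 1.0 and 1.3 x REE"). On the covariance: "An unstructured variance-covariance form among the repeated measurements will be assumed for each outcome". The estimated standard errors are then used to "perform statistical tests and construct 95% confidence intervals", and the tests on the means are these: "T-tests will be used to compare the pairwise differences between the model-based treatment means (least-squares means) at each time point". The section adds that "statistical tests will be 2-sided".

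For these comparisons the section names no overall arm or arm-by-time test, no primary day or contrast, no multiplicity adjustment, and no method for degrees of freedom or small-sample standard errors. The only multiplicity control in the plan is the false discovery rate for metabolomic features under Aim 3.

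On size, the Abstract says: "A total of 60 patients will be studied (20 per energy dose group"). Data Collection, item B, has SOFA scored on ICU days only. The inclusion criteria ask for an expected ICU stay of at least 72 hours. The adverse event section describes this population as having high mortality. No number expected to remain at any visit is given.

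**The concern.** Two separate things can mislead a reader of the results.

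The first is the number of tests. With 18 chances per outcome, and an open-ended list of laboratory outcomes, an isolated significant day is easy to find when the energy doses do not differ.

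The second is precision at late visits. The unstructured matrix has 21 parameters, estimated from at most 60 patients and from fewer at each later visit. If its estimate is treated as if it were known, and the degrees of freedom do not reflect how few patients inform days 21 and 28, standard errors there are understated and nominal 95% intervals cover less than 95%.

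The pilot is meant to inform later Phase III trials. A spurious late difference between doses in SOFA or glucose could colour how those trials are designed.

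**Working it through.** The plan states no error rate or test count for this analysis, so there is no figure of its own to reproduce.

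**Inputs from the plan.** 3 arms; 6 days; 60 patients, 20 per arm; two-sided tests; unstructured covariance; model standard errors.

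**Assumptions (not in the plan).** Alpha 0.05 per test, inferred from the 95% intervals; REML; 57 degrees of freedom (60 - 3); within-patient correlation 0.3 to 0.9, constant across visits or decaying (AR(1)); dropout completely at random at the rates shown below.

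**Step 1, counts.** Pairs: 3 x 2 / 2 = 3. Tests: 3 x 6 = 18, or 3 x 5 = 15 without day 0. Covariance parameters: 6 x 7 / 2 = 21. Expected false positives with complete data: 18 x 0.05 = 0.9 per outcome.

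**Step 2, ceiling if the tests were independent.** 1 - 0.95^18 = 60.3%; 1 - 0.95^15 = 53.7%. The tests are not independent: the three pairs share arms and the visits share patients.

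**Step 3, complete data.** With a separate mean for every arm and day, the least-squares-mean difference is the plain difference in arm means. Its REML variance is the pooled within-arm variance on 57 df. Each t-test is therefore exact at 5% for normal data; 20,000 null trials per setting gave 4.7-5.1% at day 28. The chance of at least one false difference, from 20,000 null trials per setting, was:

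| Within-patient correlation | Any of 18 | Any of 15 (no day 0) |
|---|---|---|
| 0.3 | 50-52% | 44-46% |
| 0.5 | 43-49% | 39-43% |
| 0.7 | 35-42% | 33-37% |
| 0.9 | 24-29% | 23-26% |

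**Step 4, dropout.** Null trials were fitted with the unstructured model, model standard errors and 57 df. The rows with 100%, 40% and 20% left use 800 trials per setting and correlations 0.3-0.7. The rows with 35% and 25% left use 700 trials per setting and three correlation patterns.

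| Left at day 28 | Day-28 error per test | Any of 18 |
|---|---|---|
| 100% | 4-6% | 37-52% |
| 40% | 8-10% | 46-59% |
| 35% | 8-12% | 50-59% |
| 25% | 14-16% | 57-67% |
| 20% | 17-23% | 61-72% |

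A smaller run of 300 trials gave 13% per test at day 28 with 25% left. The 40% row assumes 100/100/90/70/50/40% left at days 0/3/7/14/21/28, and the 20% row assumes 100/95/80/50/30/20%. At day 21 the error per test was 6-8% and 9-12% in those two patterns. Simulated trials were skipped, mainly because an arm had fewer than two completers, in about 10% of cases at 25% left and 19-20% at 20% left. The last two rows are therefore rougher.

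**Step 5, reading the intervals.** Coverage is 100% minus the error per test. Day-28 intervals labelled 95% cover about 88-92% with 35-40% left (100 - 12 and 100 - 8), and about 84-87% with 25% left (100 - 16 and 100 - 13).

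**Step 6, Monte Carlo error.** Near 50%, 800 trials give a standard error of sqrt(0.5 x 0.5 / 800) = 1.8 percentage points.

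**The case against.** The strongest reply is that little rests on these tests. This is a 60-patient pilot. The primary endpoint is the infection rate, the listed SOFA endpoint is the mean ICU score, and day-specific glucose is not a listed endpoint. No decision rule uses a day-specific contrast, and leaving supporting comparisons unadjusted in a pilot is defensible. This stands. It limits the weight of the point and makes the overall-test gate partly a matter of judgement. It does not answer the narrow late intervals, because an interval labelled 95% should cover 95% in exploratory work too.

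Several stronger readings are tempting, and the documents do not support them.

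- A reader might infer a fixed even chance of a false difference. The figure depends on within-patient correlation and retention, and the plan gives neither.
- A reader might blame the unstructured matrix for most of it. With complete data the excess comes from the number of tests alone.
- A reader might think the tests are liberal even with complete data. Under REML and 57 df they are not.
- A reader might assume few patients are left for both outcomes. For SOFA this is a fair inference from scoring on ICU days only. For glucose it is weaker: data entry continues after transfer to the ward, and the plan sets a ward glucose goal.

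**Conclusion.** The point holds as a minor one. The plan makes 18 unadjusted tests per outcome, 15 of them after baseline.

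With complete data, the chance of at least one false difference per outcome is about 25-50% as within-patient correlation goes from 0.9 down to 0.3, while each test stays at 5%.

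With dropout, day-28 error per test rises to about 8-12% with 35-40% of patients left, and to about 13% or more with 25% or fewer left. The chance of at least one false difference rises to about 46-59% with 35-40% left, and higher with fewer.

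All of this assumes alpha 0.05, REML, 57 df and dropout completely at random. A different degrees-of-freedom method would change the late-visit figures. Analysing two or more outcomes this way raises the overall chance further. The consequence is confined to how single significant days and late intervals in SOFA and laboratory measures may be read. The primary endpoint and the mean ICU SOFA endpoint are not affected.

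**What to change.** Three changes to the repeated-measures paragraph under For Aim 1:

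1. Name the Kenward-Roger method for standard errors and degrees of freedom. It targets both sources of the late-visit problem; its effect was not simulated here.
2. For each outcome, test arm once with a single joint test over days 3 to 28, which has 2 x 5 = 10 numerator degrees of freedom. Treat day-specific pairwise results as descriptive estimates with intervals unless that test is significant. Use one joint test, because passing on either an arm or an arm-by-time test would loosen the gate. When no arm differs at any visit, the gate holds the chance of any false claim for that outcome to about 5%.
3. Drop the day-0 pairwise tests. They compare randomised baselines, and the plan already compares baseline SOFA and glucose by arm with another test. By themselves they add about 1-6 percentage points to the false-difference figures.

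The cost is one software option and a sentence or two, with no new data. The downside is slightly wider intervals and fewer day-specific claims. If the sponsor prefers no gate in a pilot, items 1 and 3 are still worth making, with the day-specific results labelled descriptive.

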The increasing rate of hospital-acquired infection and sepsis are major causes of morbidity and mortality in intensive care unit (ICU) patients ^{1, 2}. The enormous impact of critical care-related illness demands that we find cost-effective therapies to improve outcome that can be rapidly implemented. Malnutrition is also very common in critically ill patients and is associated with increased hospital-acquired infections and mortality in ICU patients ³⁻¹³. Protein and/or energy deficits are associated with increased rates of hospital infection, skeletal muscle weakness, impaired wound healing, and prolonged convalescence in ICU patients ^{12, 14-17 3, 34-37}. To prevent or treat malnutrition, enteral nutrition EN and/or PN are routinely given worldwide to a significant proportion of ICU patients ³⁻¹³. **Unfortunately, very few well-designed RCTs on the clinical efficacy of specialized nutrition support modalities in critical illness have been performed** ^{18, 19}. Observational studies indicate that initial nutritional goals in ICU settings are infrequently achieved; recent surveys show that both underfeeding, and, to a lesser extent, overfeeding, are common in ICU settings ^{5, 7, 20-22}. Unfortunately, rigorous, prospective studies to determine effects of different energy doses have not been performed ^{5, 7, 12}. The comparative efficacy of energy doses in critically ill patients is thus unknown and clinical recommendations are conflicting and controversial; this issue is the focus of our application. Given the changes in the methods of ICU nutritional support during the past 5-10 years, including tighter blood glucose control ^{23, 24} and the use of overall lower caloric loads than in previous decades (when “hyperalimentation” was the norm), there is a clear need for further CER studies of different modalities of nutrition support based on current ICU clinical care practices ²⁵⁻³¹. Energy (calorie) needs in adult patients in the ICU often vary considerably because of day-to-day changes in clinical conditions ^{9, 32, 33}. However, optimal caloric requirements in critically ill patients are unknown due to a lack of rigorous RCTs. The resting energy expenditure (REE), or basal metabolic rate, is best determined using serial bedside metabolic cart measurements (indirect calorimetry), but technical issues (e.g. air leaks, high inspiratory oxygen concentration) can cause inaccuracies ^{3, 32, 33}. REE can also be estimated using standard equations, most commonly the Harris-Benedict equation (HBE), which incorporates the patient's age, gender, weight, and height ^{3, 10, 12}. Unfortunately, the HBE may over- or underestimate REE in critically ill patients ^{3, 32, 33}.

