cardiac death⁴⁵⁻⁴⁹. Fractal analysis of metabolomic data will allow us to test whether the Hurst exponent is related to clinical outcomes and/or response to nutritional interventions in the ICU patients we propose to study.

Emerging data strongly suggest that microbes of the intestine (the microbiota) play a key role in host metabolism, immune/inflammatory processes and disease pathophysiology⁵⁰⁻⁵². The intestinal microbiome (genome of the gut microbiota) is shaped by both environment (e.g. diet) and host genetics; and, vice versa, the gut microbiota itself appears to regulate a wide spectrum of host immune, inflammatory and metabolic responses⁵³. **Human data on the impact of nutrition support during critical illness on the gut microbiome are limited.**

Despite limited evidence, there is a suspected interplay between critical illness and the gut microbiome, which warrants further exploration in the setting of nutrition support⁵⁴⁻⁵⁸. Nelson et al utilized 16S rRNA pyrosequencing to characterize stool of hospitalized patients and observed perturbations in gut microbiota following infection⁵⁹. It is acknowledged that the microbiome plays an integral role in health maintenance, and that modifications of the gut microorganisms may influence outcomes in critically ill patients.

Hypothesis:

- 1) Adequate energy administration (defined as 1.3 x REE) will result in a lower 28-day total hospital-acquired infection rate compared with ICU patients receiving lower energy doses.
- 2) Differences in energy intake will result in global changes in metabolic patterns that themselves are associated with clinical outcomes in the ICU patients studied.

Specific Aims:

- 1) To perform a controlled, double-blind, prospective, randomized, parallel group, intent-to-treat Phase II clinical trial to test the efficacy of three specific energy doses [0.6, 1.0 and 1.3 x measured REE (metabolic cart), respectively], given for 28 consecutive days during the ICU course, on 28-day total hospital-acquired infections (primary endpoint), BSI, and other important clinical outcomes in medical/surgical ICU patients requiring specialized parenteral ± enteral feeding.
- 2) In Aim 1 subjects to: a) examine the impact of cumulative and mean daily 28-day energy deficits [energy intake-measured REE] on clinical outcome endpoints; and b) to estimate the agreement for REE as determined by the HBE and the measured REE across different energy doses.

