Study Schema: Controlled, randomized, double-blind, prospective, parallel-group, intent-to-treat **Aim 1** clinical trial to test the efficacy of three energy doses [0.6, 1.0, and 1.3 x measured REE (MREE), by metabolic cart, respectively], given for 28 consecutive days during the ICU and post-ICU course in critically ill medical and surgical patients requiring parenteral nutrition (PN) ±enteral nutrition (EN) at Emory University. The primary endpoint is total hospital-acquired infections after entry; secondary endpoints are bloodstream infections, ventilator-free days, and ICU and 28-day hospital length of stay and mortality. **Aim 2** examines the effect of cumulative and mean daily measured 28-day energy deficits after entry on Aim 1 clinical outcome endpoints and relationships between estimated REE (Harris-Benedict equation) at study entry. **Aim 3** explores the impact of energy dose and cumulative and mean daily 28-day energy deficits on global metabolomic patterns, microbiome, and strength over time and in association with key clinical outcomes in Aim 1.

↑ Plasma (metabolome), microbiome, and strength analysis

Data Collection: Baseline data collected will include APACHE II score, and clinical and demographic data. The following will be collected during the course of the study:

A) Measured resting energy expenditure (MREE; per metabolic cart) will be determined on the baseline day before 2 pm. The goal energy dose composition of PN for all three energy doses for each enrolled subject is calculated by the blinded research team members. The metabolic cart-derived REE will be used to determine basal energy expenditure (REE) and thus the initial energy dosing^{5, 10, 12}. MREE will be determined at baseline and 5x weekly (M-F before 2 pm; see Aim 2) using a state-of-the-art metabolic

cart and standard methodologies by a study team respiratory technician with prior experience and expertise in clinical indirect calorimetry. In the event that the metabolic cart is not available, the most recent measurements will be used. The nutrition will not be adjusted if the MREE is <10% changed from the reading the day before.

- B) Longitudinal SOFA scores of organ dysfunction/failure: Sequential organ failure assessment (SOFA) scores will be calculated in the morning of each ICU day ⁶⁰. The baseline Apache II score on the day of ICU admission will also be calculated in all patients.

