For Aim 2: The agreement between the study entry HBE and the initial REE, as well as the mean daily serial MREE by metabolic cart, will be summarized using graphical methods and by calculating the 95% limits of agreement estimated by the mean difference ± 1.96 standard deviation of the differences. Bland and Altman (1999)⁶³ extend the limits of agreement approach to data with repeated measurements (i.e., serial REE measurements). To investigate whether the relationship between mean daily serial REE and entry HBE is altered by the mean daily caloric dose administered, regression methods will be used (i.e., analysis of covariance, ANCOVA). ANCOVA analyses will also be stratified by location (ICU versus the floor).

For Aim 3: The data processing will be performed as follows: 1) Feature detection conducted by systematic re-extraction with multiple parameter settings that optimize sensitivity and reliability; 2) Sample quality and feature consistency evaluation; 3) Feature overlap detection between datasets; 4) Statistical analysis includes false discovery rate (FDR; typically with $q=0.05$) to identify significantly different features between the two groups while correcting for multiple comparisons; hierarchical cluster analysis (HCA) to visualize differences between groups as

well as between time points and to identify clusters of highly correlated features that can be mapped to biological pathways; 5) Characterization of features and biological pathways utilizing multiple chemical databases (KEGG) metabolic pathways

(http://www.genome.jp/kegg/tool/color_pathway.html), MetaCore (www.genego.com; Carlsbad, CA), and MetaCyc (<http://www.metacyc.org>).⁶⁹ We will utilize Metaboanalyst 2.0⁷⁰ for the time series analysis to detect metabolic changes throughout the study period and two-way ANOVA to determine the impact of varying energy doses on global metabolomics patterns. Once important features have been identified, we have the ability to positively identify the chemical names of known metabolites by MS/MS analysis.

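### The Aim 2b ANCOVA does not name initial measured REE or fix the dose scale: coded as randomised group it loses precision, coded as delivered kcal/day it can create a spurious dose effect

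*Combined protocol and SAP*

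**What the plan says.** Aim 2(b) under Specific Aims is "to estimate the agreement for REE as determined by the HBE and the measured REE across different energy doses". The Statistical Analysis section, For Aim 2, serves it in two ways. Limits of agreement are planned for "The agreement between the study entry HBE and the initial REE, as well as the mean daily serial MREE by metabolic cart". A regression, named as ANCOVA, then asks whether "the relationship between mean daily serial REE and entry HBE is altered by the mean daily caloric dose administered", and is repeated separately for ICU and floor.

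The regression is only outlined. There is no model equation, no full covariate list, no scale for dose (assigned multiple, kcal/day or kcal/kg), and no statement of whether the tested term is a dose main effect or an HBE-by-dose interaction.

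Four other places bear on it:

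- Data Collection, item A: "MREE will be determined at baseline and 5x weekly". The initial reading is therefore planned for everyone.
- Background: "the HBE may over- or underestimate REE in critically ill patients".
- Hospital nutrition support: calories start as a multiple of baseline measured expenditure and are then re-set from serial cart readings during the ICU stay. Item A adds that changes under 10% do not trigger an adjustment.
- Potential Risks: the three doses are described as multiples of REE estimated by HBE, whereas the Abstract, Data Collection and the nutrition section use measured REE.

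**The concern.** The plan accepts that HBE can be wrong for an individual in either direction. That personal error exists before study feeding starts and carries through into every later cart reading. The baseline cart reading measures it, with noise. The plan uses that reading in the limits of agreement but does not name it in the regression.

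Two different harms can follow, depending on how dose is coded.

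- **Randomised multiple.** Randomisation makes the multiple independent of HBE error, so the dose estimate is unbiased. The error inflates the residual, and with 20 patients per arm a real effect may be missed.
- **Delivered kcal/day**, the plainest reading of a caloric dose administered. Calories are a multiple of measured REE. A patient whose REE exceeds HBE has both a higher outcome and more calories, so dose and outcome are correlated even if feeding does nothing to REE.

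The first coding can hide a real effect and the second can manufacture a false one. As written, the plan allows either.

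**Working it through.** **Inputs from the documents.** 60 patients, 20 per arm; dose levels 0.6, 1.0 and 1.3; tests two-sided (stated for Aim 1). No SD, effect size, alpha or power is given for Aim 2, so there is no planned figure to reproduce.

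**Assumptions.** Patient-level HBE-error SD τ = 100 to 250 kcal/day; day-to-day SD of a cart reading σ = 150 or 250; later drift in REE with SD 100; 3 to 15 readings per patient (8 in the closed form); alpha 0.05; full delivery of the assigned dose; normal errors.

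**1. Dose as randomised multiple: residual variance.**

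Without initial REE: V0 = τ² + 100² + σ²/8.

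With initial REE: V1 = V0 − τ⁴/(τ² + σ²).

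SE of a 20 v 20 difference = √(2V/20).

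| τ / σ | V0 | τ⁴/(τ²+σ²) | V1 | Reduction | SE, kcal/day |
|---|---|---|---|---|---|
| 100 / 150 | 22,812 | 3,077 | 19,736 | 13% | 47.8 to 44.4 |
| 200 / 250 | 57,812 | 15,610 | 42,203 | 27% | 76.0 to 65.0 |
| 250 / 150 | 75,312 | 45,956 | 29,357 | 61% | 86.8 to 54.2 |

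Simulated power for a 120 kcal/day difference between the 0.6 and 1.3 arms, without and with initial REE:

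- 100/150: 67% to 74%
- 200/250: 34% to 43%
- 250/150: 26% to 54%

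Type I error was about 5% throughout. Testing HBE × dose instead gave similar gains (33% to 42% at 200/250; 27% to 57% at 250/150).

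**2. Dose as delivered kcal/day: rejection rate with no true dose effect.** Under the same settings, with kcal = multiple × serial REE, the planned main-effect model rejected in 64-98% of trials, and in 59-86% after initial REE was added.

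A second grid (cart-error SD 100, HBE mean 1600 and SD 250, 3,000 trials per row) separates the two ways in which kcal could follow REE:

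| HBE-error SD / drift SD | kcal from initial REE: without, with covariate | kcal from serial REE: without, with covariate |
|---|---|---|
| 100 / 100 | 20%, 5% | 58%, 46% |
| 150 / 100 | 45%, 5% | 78%, 50% |
| 250 / 150 | 88%, 5% | 99%, 76% |
| 350 / 200 | 98%, 5% | 100%, 89% |

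The false slope in the planned model is positive, from 0.04 to 0.40 kcal of REE per kcal of dose. The planned dosing starts from baseline REE, is re-set in the ICU and ignores changes under 10%, so it should lie between the two columns. If kcal were a multiple of HBE, rejection stayed near 5% and only precision was lost, as in step 1.

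**3. Effect of the covariate on the HBE slope.** Let serial REE have true slope b on HBE, and let L = τ²/(τ² + σ²). With the covariate written as (initial REE − HBE), the HBE coefficient becomes b − L(b − 1). For b = 0.7 this is 0.7 + 0.3L:

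- 100/150: L = 0.308, coefficient 0.79
- 200/250: L = 0.390, coefficient 0.82
- 250/150: L = 0.735, coefficient 0.92

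The slope is pulled towards 1, which would hide proportional miscalibration of HBE. If initial REE is entered undifferenced, the coefficient is b(1 − L) instead. The dose estimate is identical in both forms, and in neither is the HBE coefficient the calibration slope unless, in the differenced form, b = 1.

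**The case against.** This is a secondary agreement aim in a pilot designed "to generate critical preliminary data needed to inform subsequent appropriately powered Phase III multicenter trials", with no power claim for Aim 2. The regression is a sketch, so not naming a covariate does not rule it out. A trialist may also want the effect of calories actually received, which the randomised group does not measure when delivery is incomplete.

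Much of this stands. The fair statement is that the plan does not name initial REE, not that it excludes it. The primary endpoint is untouched. Delivered dose is a legitimate interest, but it belongs in an exploratory analysis, because here it is computed from the outcome variable. The pilot argument does not excuse the kcal/day problem: a spurious association is poor preliminary data at any sample size.

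Three stronger readings are tempting and are not supported:

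- A reader might infer that HBE error swamps the dose effect. The documents give neither the error SD nor an expected effect, and at an assumed SD of 100 the power loss is small (67% against 74%).
- A reader might infer that the precision argument holds on any dose scale. It does not: with kcal/day the error moves into the dose term and the harm reverses direction.
- A reader might infer that adding initial REE repairs the model and leaves the HBE slope interpretable. Steps 2 and 3 show otherwise.

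**Conclusion.** The point holds in a conditional form. With dose as the randomised multiple, leaving out initial REE costs precision only, and the cost runs from small to large: 7, 9 or 28 percentage points of power for a 120 kcal/day effect across the assumed SDs. With dose as delivered kcal/day tracking serial REE, the planned main-effect model gives a false dose effect in most simulated trials, and the extra covariate does not cure it. It does so only if calories follow the initial reading alone.

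All sizes rest on assumed SDs, full delivery and complete cart data. The direction of each result does not depend on the particular SDs. Which case applies turns on the dose coding, which the plan leaves open, and on the dose base, which it states in two ways.

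**What to change.** In the Statistical Analysis section, For Aim 2:

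- Make the randomised energy-dose group the dose term, with entry HBE and initial cart-measured REE as covariates.
- State whether the test is the dose main effect or HBE × dose.
- Label any analysis of delivered kcal as exploratory, and note that calories are set from measured REE.
- Report the HBE slope and the HBE-REE calibration from the model without initial REE.
- Use the same terms in the ICU and floor analyses.
- Keep patients without a baseline reading in an unadjusted sensitivity analysis.

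Separately, reconcile the description of the dose base in Potential Risks (HBE-estimated REE) with the Abstract, Data Collection and nutrition sections (measured REE).

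The cost is one degree of freedom for the covariate and a few lines of SAP text. No new data are needed.
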